- Primary molars with mobile teeth, arrested caries, restored teeth, non-vital teeth, no carious lesion, presence of developmental defects and non-restorable teeth.
- Patients on any antibiotic regimen either on the day of treatment or for at least 2 weeks prior to the study.
- Patients allergic to Latex.
- Radiographic evidence of external or internal root resorption, furcal or periapical radiolucency.
- Primary molars with more than half of the root length resorbed.
- Children who did not attend and complete the second session of treatment.
- Not approving to sign the consent.

Sample Size Calculation:

The sample size was measured using G power analysis for calculating estimated sample size.

Based on the results of Bohari et al. 2012, it was found that 30 subjects per group were required

to detect a statistically significant difference between the two groups anxiety score (FLACC) with a power of 95% at the significance level of 0.05.

The study group will be consisted of 120 primary molars with bilateral design from 60 children aged 4-9 years without sex predilection. The included teeth will be assigned randomly into one of the following groups according to the decay removal technique that will be utilized using two-arm parallel groups with split-mouth design:

The control group (A): (n=60) primary molars will be subjected to removal of caries using a conventional drilling method using carbide dental burs.

The test group (B): (n=30) primary molars will be subjected to removal of caries using a chemo-mechanical agent (Brix3000[®], Brix Medical Science, Carcarañá-Santa Fe, Argentina).

The test group (C): (n=30) primary molars will be subjected to removal of caries using a chemo-mechanical agent Carie-Care[™], Uni-Biotech Pharmaceuticals Private Limited, Chennai, India in collaboration with Vittal Mallya Scientific Research Foundation).

Armamentarium & Equipment

- 1) Basic dental examination Kit
- 2) Restorative kit
- 3) Brix3000[®] “Brix Medical Science, Carcarañá-Santa Fe, Argentina”
- 4) Carie-Care[™] “Uni-Biotech Pharmaceuticals Private Limited, Chennai, India in collaboration with Vittal Mallya Scientific Research Foundation”.
- 5) Dental bur “Low-Speed Tungsten Carbide round bur US-NO 1-8, Meisinger, USA. L.L.C., [name]; High-Speed Diamond round medium size 08-018, Meisinger, USA. L.L.C., [name]”

- 6) Rubber dam kit.
- 7) Sterile vial.
- 8) Bacteriological incubator

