- 9) Inoculation loop.
- 10) Blood agar plates “Schaedler agar”
- 11) GC Fuji IX GP®.
- 12) A Stop Watch.

Methods:

Study design

Experimental, randomized controlled clinical trial with two-arm parallel groups and bilateral design following the “Consolidated Standards of Reporting Trials (CONSORT,2010)” statement (Fig.3).

Randomization

Since bilateral technique will be utilized in both parallel groups, it was decided to start on the right side irrespective of the method assigned by randomization. To control the variable of the side favored by the clinician, the researchers will make sure that each side is treated evenly by both methods using block randomization. Before recruiting participants, 60 sealed envelopes containing the randomization results will be arranged, sealed and mixed blindly in a box. Each envelope represents a block of the two contralateral teeth. The envelopes will be numbered blindly from 1 to 60. Each envelope will be opened immediately before starting the procedure on the right side.

[figure not shown]

Figure 3: Flow diagram of the Study

Clinical Procedures

The degree of dental destruction will be clinically determined by using a dental probe. Only open occlusal cavities with brown and softened dentin with broadly comparable depth exhibiting frank moderate cavitation will be chosen “severe decay, stage 5, ICDAS [International Caries Detection and Assessment System]” (Ismail et al., 2007, Dikmen, 2015). The depth of caries progression will be confirmed with an intraoral periapical radiograph such that radiolucency did not involve the pulp.

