The carious cavity will be treated with Carie-Care™ “Uni-Biotech Pharmaceuticals Private Limited, Chennai, India in collaboration with Vittal Mallya Scientific Research Foundation”. Following the instructions of the manufacturer, the Carie-Care™ gel will be brought to room temperature. The gel will be left in the carious lesion for 60 seconds. At that time, the appearance of the gel will be changed from translucent into cloudy. Then the gel will be removed with moistened cotton pellet and softened carious dentin will be scrapped off using spoon excavator ((Size #2, #3, #4; Nordent Manufacturing Inc., [name]). The process will be redone till consecutive administration of the gel was unsuccessful to turn into cloudy. Decay removal will be verified by probing with dental explorer (visual-tactile clinical criteria).

Statistical Analysis

The statistical assessment will be carried out using Statistical Package for Social Sciences (SPSS, V.20, IBM; Armonk, NY, USA). Analysis of data will be done through measuring *p*-value to determine statistical significance. The level of significance will be set at 0.05 (*p*-value of less than 0.05 was considered statistically significant). Various statistical methods will be used for measuring *p*-value depending whether the data will be normally distributed (parametric) or not normally distributed (non-parametric). For normally distributed data, paired sample t-test and independent sample t-test will be used. For non-normally distributed data, Wilcoxon signed rank test and Mann Whitney U test will be used.

Wong-Baker FACES® Pain Rating Scale

[figure not shown]

Figure 4: Wong-Baker FACES® Pain Rating Scale.

RESEARCH LIMITATIONS

Although, the chemo-mechanical methods cannot eliminate the dental caries completely, it tends to follow the principles of minimal intervention dentistry approaches. The generalization of results is one of the expected limitations of this research.

STRUCTURE OF THE RESEARCH

The research will be divided into several chapters:

- Chapter 1 will represent the introductory note on the state of dental caries among children and treatment approaches that are extensively used by the dentists including different chemo-mechanical agents used.
- Chapter 2 will present the literature review for the study.

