- Chapter 3 will depict the methodology for the research. It will provide in-depth explanation of the materials and methods used for gathering data regarding different treatment modalities used in this research.
- Chapter 4 will illustrate the results attained from this research.
- Chapter 5 will provide the discussion of findings on the basis of results obtained in the research.
- Chapter 6 will sum up the entire results with general conclusions, evaluation of hypothesis, policy implications, and recommendations.

THESIS PLAN

STEPS OF PhD THESIS	TIME FRAME (MONTH)											
	1	2	3	4	5	6	7	8	9	10	11	12
Application of CONSORT Statement 2010	X											
Proposal writing		X										
Proposal presentation			X									
Discussion with the statistician		X										
Ethical approval				X								
Registration					X							
Apply for funding					X	X						
Providing tools and materials							X					
Intervention for in-vivo study							X	X	X			
Intervention for in-vitro study							X	X	X			
Data analysis									X	X	X	
Thesis writing									X	X	X	
Thesis defense												X

EXPECTED FINDINGS

The findings may show an increased efficacy, efficiency with decreased pain experienced during caries removal of chemo-mechanical method using newly developed agent (Brix3000[®]) as the manufacturer company claimed compared to the previously-available (Carie-CareTM) and to the conventional surgical method. It may be recommended as an alternate treatment modality among children, who fear to visit clinics for getting dental treatments.

REFERENCES

Anusavice KJ, Kincheloe JE (1987). Comparison of pain associated with mechanical and chemomechanical removal of caries. J Dent Res.66:1680–1683.

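### Brix3000 v Carie-Care is a 30 v 30 comparison between children with no assigned test; adjusting for each child's own drilled tooth would be a cheap gain in precision.

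*Combined protocol and SAP*

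**What the plan says.** Sample Size Calculation describes 60 children and 120 molars in "two-arm parallel groups with split-mouth design": 60 drilled molars, 30 treated with Brix3000 and 30 with Carie-Care. Under Randomization, "Each envelope represents a block of the two contralateral teeth". Each child therefore supplies one drilled tooth and one gel tooth, and the two gels are never used in the same child.

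Statistical Analysis states "For normally distributed data, paired sample t-test and independent sample t-test will be used", with Wilcoxon signed rank and Mann-Whitney U as the non-normal counterparts, and "The level of significance will be set at 0.05". It links none of the four tests to a comparison or an outcome. It does not say whether an independent test would use raw gel-tooth values or within-child differences. No covariate-adjusted or mixed model is listed.

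Brix3000 v Carie-Care falls under the null hypothesis, which covers both gels and drilling. Expected Findings looks for better results with Brix3000 "compared to the previously-available (Carie-CareTM) and to the conventional surgical method". The three Research Objectives set the gels against drilling. Clinical Procedures records bacterial count, time and pain in all groups, and takes a dentin sample from the lesion both before and after caries removal.

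**The concern.** The contrast between the gels is the only one of interest that cannot be made within a child. Differences between children (age 4-9, use of the pain scale, caries activity) therefore enter its error. The drilled tooth in the same mouth reflects part of that variation, on the same scale and under a treatment common to both arms, but nothing in the plan brings it into this comparison.

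At stake are precision and prespecification. With the choice left open, the analyst could compare raw values or within-child differences. Their power can differ a good deal, and which does better depends on a correlation that will be known only from the trial's data.

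**Working it through.** **The plan's own figure.** Sample Size Calculation says "it was found that 30 subjects per group were required", "with a power of 95% at the significance level of 0.05", for an anxiety score. No effect size or SD is given, so 30 cannot be reproduced. Solving backwards (two-sided, normal approximation): d = (1.960 + 1.645) × √(2/30) = 3.605 × 0.2582 = 0.93 SD. A t-based calculation gives 0.95. Neither can be checked against the documents.

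**Inputs.** From the documents: 30 children per gel and alpha 0.05. Assumed: a two-sided test (sidedness is not stated), equal SDs for gel and drilled teeth, rho from 0 to 0.7, and a gel difference of 0.5 SD for illustration.

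**Formulas.** Let f be the variance of the gel contrast relative to the raw comparison.
- Raw gel-tooth values: f = 1.
- Gel-minus-drill differences: f = 2(1 - rho).
- Drilled-tooth outcome as covariate: f = 1 - rho².
- Equivalent children per arm with the covariate: 30 / (1 - rho²).
- Power: Φ(0.5 / √(2f/30) - 1.96).

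Example, covariate at rho 0.5: f = 0.75; √(2 × 0.75/30) = 0.2236; 0.5/0.2236 = 2.236; 2.236 - 1.96 = 0.276; power 61%. Raw: 0.5/0.2582 = 1.936; 1.936 - 1.96 = -0.024; power 49%.

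| rho | f, covariate | equivalent per arm | power raw | power differences | power covariate |
|---|---|---|---|---|---|
| 0 | 1.00 | 30 | 49% | 28% | 49% |
| 0.2 | 0.96 | 31 | 49% | 33% | 51% |
| 0.3 | 0.91 | 33 | 49% | 37% | 53% |
| 0.5 | 0.75 | 40 | 49% | 49% | 61% |
| 0.7 | 0.51 | 59 | 49% | 71% | 77% |

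Because 1 - rho² = (1 - rho)(1 + rho) and 1 + rho ≤ 2, the covariate factor never exceeds the differencing factor. Differencing beats raw values only when 2(1 - rho) < 1, that is, rho > 0.5.

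**Simulation check** (4,000 trials per setting, 30 per arm, 0.5 SD; raw / differences / covariate):
- rho 0: 47.6% / 28.0% / 47.1%
- rho 0.3: 47.8% / 36.3% / 50.4%
- rho 0.5: 47.0% / 47.6% / 58.3%
- rho 0.7: 47.0% / 69.1% / 75.6%

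With no true difference, all three methods rejected in 4.6% to 5.2% of trials. At rho 0 the covariate cost 47.6 - 47.1 = 0.5 points.

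**On the plan's scale.** The difference detectable with 95% power falls from 0.93 SD to 0.93 × √(1 - rho²): 0.91, 0.89, 0.81 and 0.67 SD at rho 0.2, 0.3, 0.5 and 0.7.

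**The case against.** A reader might infer that the plan commits to comparing raw gel-tooth values and ignores the drilled tooth. The documents do not say so. No test is assigned, and an independent t-test or Mann-Whitney test on within-child differences is among the listed methods and would use the drilled tooth. What stands is that the analysis is unspecified and that the most efficient simple option is not listed.

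A reader might also treat this contrast as the trial's headline. That goes too far: the objectives compare the gels with drilling, where the listed paired tests already use the pairing, and Expected Findings names both comparisons.

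The strongest objection concerns size. The documents do not give rho, and at 0.2 to 0.3 the gain is only 4% to 9% of variance, or 1 to 3 children per arm. That is fair, and it rules out any claim of proven material waste. The case rests on asymmetry: almost nothing is lost at rho 0, and 10 children per arm are gained at 0.5.

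Three cautions about the remedy also stand. Counts and times are likely to be skewed, and the plan already provides rank tests for that. For bacterial count, the gel tooth's own pre-removal sample is a true baseline and may leave less for the drilled tooth to add. And the drilled tooth is measured after randomization. The right side always goes first, so the drilled tooth sometimes follows the gel tooth, and the first experience could colour its pain score.

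**Conclusion.** The point holds as a cheap improvement. The contrast is between children, only two of the four listed tests fit it, neither is assigned to it, and no covariate adjustment is planned. The listed tests keep their 5% type I error, so a reader should not infer bias or an invalid comparison.

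The benefit is small at low correlation and substantial only if rho is about 0.5 or more. The variance factors rest on an assumed rho and a roughly linear relation between the two teeth. The power figures also assume a 0.5 SD difference and a two-sided test, and the differencing figures assume equal SDs.

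**What to change.** State in Statistical Analysis that Brix3000 v Carie-Care is tested as follows.

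- **Bacterial count and time:** a linear model of the log-transformed gel-tooth outcome on agent plus the same child's log-transformed drilled-tooth outcome, with a rank-based ANCOVA if the data remain non-normal. For count, add the gel tooth's own pre-removal count as a covariate.
- **Pain:** an ordinal model, or rank ANCOVA, with the drilled-tooth score as covariate. Do not use a test on gel-minus-drill differences, which loses power at low correlation.
- **Alternative:** a mixed model on all 120 teeth with a random child effect, only if treatment is one three-level factor with a common drilled-tooth mean and variances may differ by method. Separate drilled means for each arm would return the raw contrast.
- **Reporting:** give the unadjusted result alongside, and note that the covariate is measured after randomization and that carry-over could affect the pain score.

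The cost is analysis wording only. No new data are needed and the design does not change.
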